2.0 LIST OF ABBREVIATIONS

AE	Adverse Event
ALT	Alanine Aminotransferase
AST	Aspartate Transaminase
BMI	Body Mass Index
CABG	Coronary Artery Bypass Graft
CAM-ICU	Confusion Assessment Method for the ICU
CPOT	Critical Care Pain Observation Tool
CRF	Case Report Form
CTMS	Clinical Trial Management Software
DOS	Day of Surgery
DSMB	Data & Safety Monitoring Board
DSMC	Data & Safety Monitoring Committee
FDA	Food and Drug Administration
eCRF	Electronic Case Report Forms
ERAS	Enhanced Recovery After Surgery
GCP	Good Clinical Practice
HIPAA	Health Insurance Portability and Accountability Act
ICU	Intensive Care Unit
IMA	Internal Mammary Artery
INR	International Normalized Ratio
IRB	Institutional Review Board
MME	Morphine Milligram Equivalents
NIH	National Institutes of Health
NRS	Numeric Rating Scale
OHRP	Office for Human Research Protections
OnCore	Online Collaborative Research Environment
PACU	Post-Anesthesia Care Unit
PHI	Protected Health Information
PI	Principal Investigator
PIFB	Pecto-Intercostal Fascial Plane Block
POD	Postoperative Day
PTT	Partial Thromboplastin Time
SAE	Serious Adverse Event
SOC	Standard of Care
TPP	Transversus Thoracic Plane
UP	Unanticipated Problem
X	Applies to Research Only

[figure not shown]
3.0 STUDY SUMMARY

3.1 Synopsis

Full Title	Pecto-Intercostal Fascial Plane Block for Enhanced Recovery After Cardiac Surgery
Short Title	PIFB and Recovery After Cardiac Surgery
Protocol Number	HS IRB 2021-0111
ClinicalTrials.gov Identifier & Summary	
Pending
 
This study is being done to see if bilateral pecto-intercostal fascial plane blocks with a mixture of liposomal and standard bupivacaine decrease pain and opioid requirements in patients undergoing cardiac surgery via median sternotomy compared to controls (sham blocks with saline).

Number of Site(s)	1
Main Inclusion Criteria	
 The patient is 18-80 years old The patient's ideal body weight (IBW) is >50kg The patient is planned to undergo elective coronary artery bypass graft or single valve repair/replacement surgery via median sternotomy
Main Exclusion Criteria	
 The patient has a preoperative coagulopathy (INR >1.4, platelets <100,000) or ongoing anticoagulation or anti-platelet therapy (except aspirin 81mg) The patient has an allergy or sensitivity to amide-type local anesthetics, dexmedetomidine or ketamine The patient has severe left ventricle dysfunction (defined quantitatively as an ejection fraction of less than or equal to 35%) or right ventricle dysfunction (defined qualitatively as "severe") The patient uses chronic opioids (meaning at the time of the preoperative screening evaluation by the study team, the patient is prescribed and taking any opioid pain medication)
Objective(s)	
Primary Objective
 
 To evaluate postoperative opioid requirement within 72 hours in patients who received local anesthetics via PIFB compared to those control patients who received saline. 
Secondary Objectives
 
 To evaluate intraoperative opioid consumption in patients who received local anesthetics via PIFB compared to those control patients who received saline. To evaluate intensity of postoperative pain in patients who received local anesthetics via PIFB compared to those control patients who received saline. To evaluate duration of mechanical ventilation in patients who received local anesthetics via PIFB compared to those control patients who received saline. To evaluate return of bowel function in patients who received local anesthetics via PIFB compared to those control patients who received saline. To evaluate postoperative delirium in patients who received local anesthetics via PIFB compared to those control patients who received saline. To evaluate length of hospital stay in patients who received local anesthetics via PIFB compared to those control patients who received saline.

	
 To evaluate chronic opioid use at 90 days postoperatively in patients who received local anesthetics via PIFB compared to those control patients who received saline.
Endpoints	
Primary Endpoint
 
 Total daily opioid consumption during the initial 72 hours postoperatively will be measured in morphine equivalents and compared between groups. 
Secondary Endpoints
 
 Total intraoperative opioid consumption will be measured in morphine equivalents and compared between groups. Pain will be assessed, according to standard of care, every 4 hours using the 11-point Numerical Rating Scale (NRS), beginning at time 0 (arrival to ICU). Each patient's pain scores within discrete 8-hour time intervals will be averaged, and the median pain scores during each time interval will be compared between the intervention and control groups. Pain at 90 days postoperative will be surveyed by phone. Duration of mechanical ventilation will be measured by hours of mechanical ventilation after admission to the ICU. Return of bowel function will be measured in the number of postoperative days until the first bowel movement. Postoperative delirium will be measured according to standard of care by utilizing the Confusion Assessment Method for the ICU (CAM-ICU) assessment every 8-12 hours. Intensive care unit length of stay will be measured by the number of hours that the patient is in the ICU before an order is placed for transfer to a lower level of care. Duration of hospital stay will be measured by the number of post-operative days until the patient is discharged. Patient use of opioids at 90 days will be obtained by phone call.
Study Design	
This study is a prospective, single-center, randomized, double-blind, controlled trial to evaluate whether bilateral pecto-intercostal fascial plane blocks with liposomal and standard bupivacaine decrease pain and opioid requirements in patients undergoing cardiac surgery via median sternotomy compared to controls (sham blocks with saline).

Study Intervention	
The patients will be randomized to receive bilateral PIFB with a mixture of standard and liposomal bupivacaine or bilateral PIFB with saline only. Recovery characteristics, including opioid consumption, pain scores, duration of mechanical ventilation, ICU length of stay, hospital length of stay, side effects, and chronic opioid use will be evaluated.

Total Number of Subjects	
A total of 100 subjects will be recruited.

Statistical Methodology	
Data analysis will be performed on an intent-to-treat basis based upon assignment to a study arm. Continuous data will be compared using student T-test or Wilcoxon-rank sum testing as appropriate. Categorical data will be compared using Chi-square or Fisher exact testing as appropriate. The data will be presented graphically where possible using scatter plots, profile plots, or histograms. For all tests, statistical significance will be defined as a p-value less than 0.05.

Estimated Subject Duration	
The duration of the study for each subject is approximately 100 days.

Estimated Enrollment Period & Study Duration	
Study enrollment and follow-up will occur over 3 months with the total expected duration of the trial to be 24 months.

5.0 INTRODUCTION

5.1 Background

Pain after cardiac surgery via median sternotomy occurs as a direct result of surgical manipulation and tissue trauma. Acute pain is typically an inflammatory response and may be related to the surgical incision, pericardiotomy, retraction, suturing, and/or chest tube placement, among other causes. Acute pain after cardiac surgery has historically been treated with intravenous opioids, however significant side effects may limit their use and efficacy. A subset of patients experience severe acute postoperative pain, which may increase length of stay, morbidity, mortality, and healthcare costs¹. In addition, 30-50% of patients report chronic pain (lasting at least 2 months) after coronary bypass surgery², and the greatest predictor of chronic post-surgical pain is poorly controlled acute postoperative pain².

Over the past decade, with the emergence of enhanced recovery after surgery (ERAS) for cardiac surgery programs, cardiac anesthesiologists have been exploring unique options for maintenance of anesthesia and management of postoperative pain in place of high-dose opioids. Neuraxial anesthetic techniques have been used and studied extensively in this context, and while they appear safe and may even improve outcomes⁴⁻⁶, persistent concern over the rare, yet devastating, risk of spinal or epidural hematoma during full heparinization has limited their use in cardiac surgery. In addition, paravertebral blocks have shown comparable analgesic effects after cardiac surgery compared to thoracic epidural blockade⁷, however similar concerns over epidural hematoma exist.

The anteromedial chest wall, including the sternum, is innervated by the anterior cutaneous branches of the intercostal nerves. One option to target these nerves is the transversus thoracic plane (TTP) block, described by Ueshima et al, where local anesthetic is injected in the fascial plane between the transversus thoracic and internal intercostal muscles just lateral to the sternum⁸. However, the internal mammary artery (IMA) is located in the same plane, which could lead to devastating complications if this block is used for coronary bypass surgery involving the IMA.

The pecto-intercostal fascial plane block (PIFB) aims to block the anterior cutaneous branches of the intercostal nerves as they ascend in the parasternal region between the pectoralis major and external intercostal muscles. This block is superficial to the TTP and therefore should decrease the risk of injury to the IMA as well as the risk of pneumothorax. This block has been described by several different names in the literature, including the subpectoral interfascial plane block, the parasternal intercostal plane block, and the anterior thoracic medial block. Case reports and case series have demonstrated success in using this fascial plane block for acute post-sternotomy pain⁹⁻¹⁰, sternal fractures or anterior rib fractures¹¹⁻¹⁴, and as an adjunct for coverage of medial breast procedures¹⁵⁻¹⁸. Two recently published randomized controlled trials have supported this block as safe and effective for reducing visual analog scale pain scores¹⁹ and postoperative opioid requirements using standard bupivacaine injection within this fascial plane²⁰.

In 2011, the Food and Drug Administration (FDA) announced the approval of Exparel[®] liposomal bupivacaine formulation for surgical site infiltration and field blocks. It has been marketed for local nerve infiltration, hemorrhoidectomy, bunionectomy and fascial plane blocks. In 2018, the FDA expanded its indication to include interscalene brachial plexus blocks following further evidence of its efficacy and safety. One downside of single shot peripheral nerve blockade is the duration of analgesia can be relatively short lived. Exparel[®] uses the multivesicular liposomal formulation of bupivacaine to deliver an extended-release effect of local anesthetic. This extended-release action may offer the benefit of long-lasting opioid sparing effects of regional analgesia without the need for perineural catheters or repeat single-shot injections, which may be time-consuming, increase wound infection risk, and place the patient at risk of requiring repeat procedures. To that end, the use of liposomal bupivacaine in fascial plane blocks for colorectal surgery ERAS protocols has found advantages over single-shot techniques with standard bupivacaine²¹.

and similar efficacy with less opioid use compared to a catheter/epidural-based analgesic approach²². The use of liposomal bupivacaine for cardiac surgery and median sternotomy has been limited with mixed results to date²³⁻²⁴, with no studies to our knowledge evaluating its use in the PIFB.

This study aims to evaluate the efficacy of bilateral pecto-intercostal fascial plane blocks with liposomal bupivacaine in the setting of a multimodal perioperative analgesic regimen in elective cardiac surgery patients requiring median sternotomy.

5.2 Rationale

Thousands of heart surgeries are performed every day in the United States²⁵. Unattenuated perioperative pain has been shown to contribute to increased morbidity, mortality, length of stay, and healthcare costs. Practice guidelines from the American Society of Regional Anesthesiologists recommend pre-incision techniques to reduce perioperative pain²⁶, however in cardiac surgery, there are no commonly used techniques to follow this recommendation. The PIFB is a newly described fascial plane block and existing literature supports the safety and efficacy of the PIFB in cardiac surgery patients. However, there are no randomized controlled trials evaluating this technique with a long-acting depot local anesthetic.

The purpose of this study is to determine whether bilateral pecto-intercostal fascial plane blocks with liposomal bupivacaine decrease pain and opioid requirements in patients undergoing cardiac surgery via median sternotomy compared to controls (sham blocks with saline). Our primary hypothesis is that patients receiving effective regional anesthesia with liposomal bupivacaine via PIFB will demonstrate a clinically significant (25%) reduction in total daily opioid consumption through 72 hours postoperatively compared to patients receiving standard of care without effective regional anesthesia (saline only via PIFB).

6.0 STUDY OBJECTIVES AND ENDPOINTS

Objectives	Endpoints

Primary
 
To evaluate postoperative opioid requirement within 72 hours in patients who received local anesthetics via PIFB compared to those control patients who received saline.
	
Total opioid consumption during the initial 72 hours postoperatively will be measured in morphine equivalents and compared between groups.

Secondary
 
 • To evaluate intraoperative opioid consumption in patients who received local anesthetics via PIFB compared to those control patients who received saline. • To evaluate intensity of postoperative pain in patients who received local anesthetics via PIFB compared to those control patients who received saline. 	
 • Total intraoperative opioid consumption will be measured in morphine equivalents and compared between groups. • Pain will be assessed, according to standard of care, every 4 hours using the 11-point Numerical Rating Scale (NRS), beginning at time 0 (arrival to ICU). Each patient's pain scores within each postoperative day will be averaged, and the mean pain scores during each day and throughout the first 72 hours will be compared between the intervention and control groups. Maximum pain scores will also be compared between groups. Pain

	
at 90 days postoperative will be surveyed by phone.
 
 • To evaluate daily postoperative opioid consumption within 72 hours in patients who received local anesthetics via PIFB compared to those control patients who received saline.

 • To evaluate duration of mechanical ventilation in patients who received local anesthetics via PIFB compared to those control patients who received saline. 	
 • Duration of mechanical ventilation will be measured by hours of mechanical ventilation after admission to the ICU.

 • To evaluate return of bowel function in patients who received local anesthetics via PIFB compared to those control patients who received saline. 	
 • Return of bowel function will be measured in the number of postoperative days until the first bowel movement.

 • To evaluate postoperative delirium in patients who received local anesthetics via PIFB compared to those control patients who received saline. 	
 • Postoperative delirium will be measured according to standard of care by utilizing the Confusion Assessment Method for the ICU (CAM-ICU) assessment every 8-12 hours.

 • To evaluate ICU length of stay in patients who received local anesthetics via PIFB compared to those control patients who received saline. 	
 • Duration of ICU stay will be measured by the number of hours that the patient is in the ICU until an order is placed for transfer to a lower level of care.

 • To evaluate length of hospital stay in patients who received local anesthetics via PIFB compared to those control patients who received saline. 	
 • Duration of hospital stay will be measured by the number of post-operative days until the patient is discharged.

 • To evaluate chronic opioid use in patients who received local anesthetics via PIFB compared to those control patients who received saline. 	
 • Patient use of opioids at 90 days will be obtained by phone call.

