10.2.3 Postoperative Period – ICU (Visit 3)

- Opioid consumption
- Pain scores (Critical Care Pain Observation Tool [CPOT], numeric rating scale [NRS]) q 4 hours
- Time until first rescue opioid analgesia
- Time until extubation
- Time until return of bowel function
- CAM-ICU q 8-12 hours
- ICU length of stay

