12.0 STUDY ANALYSIS

12.1 Statistical Hypotheses

12.1.1 Primary Efficacy Endpoint(s):

Patients who receive local anesthetic via PIFB will demonstrate lower total opioid use during the initial 72 hours postoperatively compared to patients in the sham-control group.

12.1.2 Secondary Efficacy Endpoint(s):

- Patients who receive local anesthetic via PIFB will have a decreased intraoperative opioid requirement compared to patients in the saline-control group.
- Patients who receive local anesthetic via PIFB will have lower maximum and mean pain scores during the first 72 hours postoperatively and at 90 days postoperatively compared to patients in the saline-control group.
- Patients who receive local anesthetic via PIFB will demonstrate lower daily opioid use during the initial 72 hours postoperatively compared to patients in the sham-control group.
- Patients who receive local anesthetic via PIFB will demonstrate a significant reduction in time to extubation compared to patients in the saline-control group.
- Patients who receive local anesthetic via PIFB will demonstrate a significantly decreased time to return of bowel function compared to patients in the saline-control group.
- Patients who receive local anesthetic via PIFB will demonstrate a significantly reduced rate of postoperative delirium compared to patients in the saline-control group.
- Patients who receive local anesthetic via PIFB will demonstrate a significantly decreased ICU length of stay compared to patients in the saline-control group.
- Patients who receive local anesthetic via PIFB will demonstrate a significantly decreased hospital length of stay compared to patients in the saline-control group.
- Patients who receive local anesthetic via PIFB will demonstrate a significantly decreased persistent use of opioids at 90 days postoperatively compared to patients in the saline-control group.

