12.4 Statistical Methods

The primary endpoint is total postoperative opioid requirement within 72 hours. Total opioid requirement will be measured in morphine equivalents, presented as mean +/- standard deviation, and compared between study groups using a two-tailed independent samples t-test. Secondary outcomes (total intraoperative opioid requirement, mean and maximum 72-hour postoperative pain scores, and pain score 90 days postoperatively) will also be presented as mean +/- standard deviation and compared using independent samples t-tests. Daily postoperative opioid use and mean pain scores on POD1, POD2, and POD3 will also be compared separately with Holm-Bonferroni correction. For pain scores, we will compare mean VRS and average each patient's score within each day before averaging across days. We recognize the debate in the literature about how to analyze pain scores. In the previously referenced randomized controlled trials^{19,20}, the authors used mean scores so we will do so as well.

Continuous secondary outcomes that we expect will not be approximately normally distributed (duration of mechanical ventilation, time until return of bowel function, ICU length of stay, hospital length of stay) will be presented as median with interquartile range and compared using Mann-Whitney tests. Categorical variables (delirium, chronic opioid use) will be presented as counts or as percentages and will be compared using Fisher's exact test. For all planned comparisons with parametric tests, non-parametric equivalents will be substituted if the assumptions of parametric testing are found to be violated before testing.

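### NRS pain is averaged from ICU arrival with no rule for ventilated slots: if extubation time differs by arm, early mean pain can shift either way and the 72-hour maximum mainly against active

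*Combined protocol and SAP*

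**What the plan says.** - **Pain window.** Section 6.0 schedules an NRS pain score at 4-hour intervals, "beginning at time 0 (arrival to ICU"). The synopsis (3.1) uses the same start.
- **Summaries.** Section 6.0: "Each patient's pain scores within each postoperative day will be averaged, and the mean pain scores during each day and throughout the first 72 hours" are compared, and "Maximum pain scores will also be compared between groups". Section 12.4 makes this a 72-hour maximum, compares means by t-test, and tests POD1, POD2 and POD3 separately with Holm-Bonferroni correction. It describes the averaging as "we will compare mean VRS and average each patient's score within each day before averaging across days", so it names VRS where section 6.0 names NRS.
- **Ventilation.** Section 6.0: "Duration of mechanical ventilation will be measured by hours of mechanical ventilation after admission to the ICU".
- **Expected effect.** Section 12.1.2: active patients "will demonstrate a significant reduction in time to extubation compared to patients in the saline-control group". No size is given.
- **Second scale.** Section 10.2.3 collects "Pain scores (Critical Care Pain Observation Tool [CPOT], numeric rating scale [NRS]) q 4 hours", and 10.2.4 to 10.2.6 repeat this. CPOT appears in no endpoint and no analysis.
- **Missing data.** Section 12.5 refers to general National Research Council guidance and nothing more specific.

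**The concern.** NRS needs a patient who can answer. The pain clock and the ventilation clock start together, so early slots may hold no NRS until extubation, and extubation is itself an outcome that the block is expected to change. Randomisation and an equal 4-hourly schedule do not protect the comparison. A mean of available scores covers later hours in whichever arm is extubated later, and a maximum over more readings tends to be higher. A between-arm difference in pain could then appear, or a real one be hidden, only because the arms were scored at different hours. Pain intensity is a main secondary objective, so its interpretation is at stake.

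**Working it through.** **The plan's own figure.** Section 12.2 gives 245 ± 87 MME, a 25% reduction (0.25 × 245 = 61.25), alpha 0.05 and power 90%. Then n = 2 × (1.960 + 1.282)² × 87² / 61.25² = 42.4, so 43 per arm and 86 in total, as stated. This is the primary endpoint. No power is stated for pain, and the sample size is not affected by this point.

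**Mechanism, by hand.** The first 24 hours have six slots: 0, 4, 8, 12, 16 and 20 h. Compare a patient extubated before 4 h (scores at 4 to 20 h) with one extubated between 8 and 12 h (scores at 12, 16 and 20 h), both on the same pain course:

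- Falling 6 to 3 over 24 h: (5.5 + 5 + 4.5 + 4 + 3.5)/5 = 4.5 v (4.5 + 4 + 3.5)/3 = 4.0. Mean difference +0.5; maximum 5.5 v 4.5.
- Flat at 4.5: mean difference 0. The maximum differs only through noise over more readings.
- Rising 3 to 6: (3.5 + 4 + 4.5 + 5 + 5.5)/5 = 4.5 v (4.5 + 5 + 5.5)/3 = 5.0. Mean difference -0.5; maximum 5.5 in both.

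So the sign of the shift in the mean follows the pain course.

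**Arm-level size, by simulation with no true pain effect.** None of these inputs is in the documents: log-normal extubation times (log SD 0.5), between- and within-patient SD 1.5 each, scores rounded and bounded at 0 to 10, ventilated slots missing, day 1 taken as 0-24 h from ICU arrival. Entries are active minus control; positive is against active.

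| Pain course | Median extubation, active v control | First-24-h mean | 72-h maximum |
|---|---|---|---|
| Falling | 6 v 8 h / 4 v 10 h | +0.09 / +0.29 | +0.14 / +0.43 |
| Falling | 4 v 6 h / 6 v 10 h | +0.14 / +0.20 | +0.18 / +0.24 |
| Flat | 6 v 8 h / 4 v 10 h | 0 / 0 | +0.03 / +0.08 |
| Flat | 4 v 6 h / 6 v 10 h | 0 / +0.01 | +0.02 / +0.04 |
| Rising to 24 h | 6 v 8 h / 4 v 10 h | -0.11 / -0.35 | +0.02 / +0.04 |
| Rising to 24 h | 4 v 6 h / 6 v 10 h | -0.14 / -0.21 | 0 / +0.01 |

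The figures move with the steepness of the curve. Other curves at 6 v 8 h to 4 v 10 h reached +0.35 and -0.43 for the mean and +0.51 for the maximum. Usable day-1 readings averaged 3.8 v 3.3 at 6 v 8 h and 4.4 v 2.7 at 4 v 10 h; about 3-8% of controls had none. With equal extubation times every difference was about 0.

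**72-hour mean.** Section 12.4 averages the day means, so a first-day shift carries about one third of its size: 0.3/3 = 0.1 points.

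**If charts hold 0 for ventilated slots.** At 4 v 6 h and 6 v 10 h, the first-24-hour mean then shifts by +0.38 to +0.83 whatever the pain course. The charting rule therefore matters as much as the pain course.

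**Against the trial's precision.** With about 4 readings and 50 per arm, SE = √(1.5² + 1.5²/4) × √(2/50) = 1.68 × 0.2 = 0.34. A shift of 0.3 is just under one standard error.

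**The case against.** A reader might infer that day-1 mean and maximum pain are biased against the active arm. The documents do not support that. They give no pain course, no extubation times and no size for the hypothesised effect. The mean shifts against active only if pain falls from ICU arrival (or ventilated slots are scored 0); it is nil if pain is flat and reverses if pain rises. No day-1 maximum is planned, and the planned 72-hour maximum moves by more than 0.1 only if pain falls.

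Other objections also carry weight:

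- Section 12.4 tests POD1 without tying it to ICU arrival. If POD1 is the calendar day after surgery and arrival is at 14:00 (assumed), the POD1 shift is only +0.02 to +0.07 even with falling pain.
- It is implied, not stated, that patients arrive ventilated and that ventilated slots have no NRS.
- The synopsis defines pain by 8-hour intervals, which would largely confine the mixing of hours within each interval. Section 12.4 does not follow that definition.
- Section 12.4 acknowledges the debate on pain scores and chooses means to match earlier trials. That settles mean against median, not which hours are averaged.
- The shift is at most about one standard error, and the largest values need medians of 4 v 10 h.

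These points limit direction and size. They do not supply a rule for ventilated slots, and the general reference in section 12.5 does not either. A shift of unknown sign still makes the early pain result hard to read.

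**Conclusion.** The point holds as a conditional one. If extubation time differs by arm and ventilated slots have no NRS, section 12.4 compares different hours in the two arms. Under the assumed curves and medians of 6 v 8 h to 4 v 10 h, the early mean can be off by about -0.3 to +0.3 points, in either direction, and the 72-hour maximum by about 0 to +0.5 against active, mainly when pain is highest early. The effect is nil with equal extubation times. It is diluted to about 0.1 in the 72-hour mean and may be small for POD1, depending on how that day is defined. Only secondary endpoints are touched; the primary analysis and the sample size stand. This is a cheap improvement, not a flaw that threatens the trial.

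**What to change.** In section 12.4:

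1. Analyse NRS by scheduled 4-hour slot from ICU arrival in a mixed model, with fixed effects for slot and for arm by 24-hour period and a random patient effect. Take the daily and 72-hour contrasts from it, and keep the Holm-Bonferroni correction for the daily ones. State that the periods run from ICU arrival, and use one name for the scale.
2. Beside the 72-hour maximum, add a maximum over a clock window fixed in advance for all patients, for example 24-72 h after ICU arrival. Do not start it at each patient's extubation, which is a post-randomisation event.
3. Report CPOT by arm for intubated slots, and never pool it with NRS.
4. Report the number of scored NRS slots per arm.

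In simulation the slot-based model cut the spurious difference to 0.04 points or less in every scenario.

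The cost is a few sentences and a little more analysis on data already planned. There are two downsides. The model assumes that scores are missing at random given slot and patient; the simulations drew extubation independently of pain, so they do not test that assumption. The fixed-window maximum omits early pain, which is why it should be shown beside the 72-hour maximum and not replace it.
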